9.3 Statistical analysis

Overall survival (OS) is defined as the time from starting on trial to date of death due to any cause and progression-free survival (PFS) is defined as the duration of time from start of treatment to time of progression or death, whichever comes first. The final analysis will be conducted after the follow-time of the last patient exceeds 6 months. The primary endpoint of the study is OS at 6 month. The experimental treatment will be deemed to have good activity if ≥ 15 out of 25 evaluable patients survive 6 months or more. OS will be estimated using the Kaplan-Meier method and the two-sided 95% confidence interval (CI) for median OS will be computed using log-log transformation.

The secondary endpoints in this study include toxicity, PFS and the objective response rate (ORR) defined as (complete response (CR) + partial response (PR)) using RECIST 1.1 criteria (Appendix A). ORR will be reported with 95% CI computed by the Clopper-Pearson method. The frequency and severity of adverse events and tolerability of the regimen will be summarized using descriptive statistics. PFS with 95% CI will be estimated. As exploratory objective, the association between biomarkers and clinical outcomes (ORR, OS and PFS) will be examined using multiple logistic regression and the multivariable Cox regression model. A p-value of <0.05 will be considered statistically significant. Frequency and severity of adverse events will be summarized using descriptive statistics.

10. Data Recording

10.1 Institutional Review Board (IRB) Approval and Consent

It is expected that the IRB will have the proper representation and function in accordance with federally mandated regulations. The IRB should approve the consent form and protocol.

In obtaining and documenting informed consent, the investigator should comply with the applicable regulatory requirement(s), and should adhere to Good Clinical Practice (GCP) and to ethical principles that have their origin in the Declaration of Helsinki.

Before recruitment and enrollment onto this study, the patient will be given a full explanation of the study and will be given the opportunity to review the consent form. Each consent form must include all the relevant elements currently required by the FDA Regulations and local or state regulations. Once this essential information has been provided to the patient and the investigator is assured that the patient understands the implications of participating in the study, the patient will be asked to give consent to participate in the study by signing an IRB-approved consent form.

10.2 Data Management and Monitoring/Auditing

Data will be captured in OnCore, Moffitt's Clinical Trials Database. Regulatory documents and case report forms will be monitored internally according to Moffitt Cancer Center Monitoring Policies. Monitoring will be performed regularly to verify data is accurate, complete, and

verifiable from source documents; and the conduct of the trial is in compliance with the currently approved protocol/ amendments, Good Clinical Practice (GCP), and applicable regulatory requirements.

10.3 Adherence to the Protocol

Except for an emergency situation in which proper care for the protection, safety, and well-being of the study patient requires alternative treatment, the study shall be conducted exactly as described in the approved protocol.

10.4 Emergency Modifications

Moffitt Cancer Center and Affiliate investigators may implement a deviation from, or a change of, the protocol to eliminate an immediate hazard(s) to trial subjects without prior H. Lee Moffitt Cancer Center or their respective institution's approval/favorable opinion.

For Institutions Relying on Moffitt's IRB:

For any such emergency modification implemented, a Moffitt IRB modification form must be completed by Moffitt Research Personnel within five (5) business days of making the change.

10.5 Record Retention

Study documentation includes all eCRFs, data correction forms or queries, source documents, Sponsor-Investigator correspondence, monitoring logs/letters, and regulatory documents (e.g., protocol and amendments, IRB correspondence and approval, signed patient consent forms).

Source documents include all recordings of observations or notations of clinical activities and all reports and records necessary for the evaluation and reconstruction of the clinical research study.

Government agency regulations and directives require that all study documentation pertaining to the conduct of a clinical trial must be retained by the study investigator. In all other cases, study documents should be kept on file until three years after the completion and final study report of this investigational study.

10.6 Obligations of Investigators

The Principal Investigator is responsible for the conduct of the clinical trial at the site in accordance with Title 21 of the Code of Federal Regulations and/or the Declaration of Helsinki. The Principal Investigator is responsible for personally overseeing the treatment of all study patients. The Principal Investigator must assure that all study site personnel, including sub-investigators and other study staff members, adhere to the study protocol and all FDA/GCP/NCI regulations and guidelines regarding clinical trials both during and after study completion.

11. Ethical and Legal Aspects

11.1 Ethical and Legal Conduct of the Study

The procedures set out in this protocol, pertaining to the conduct, evaluation, and documentation of this study, are designed to ensure that the investigator abide by Good Clinical Practice (GCP) guidelines and under the guiding principles detailed in the Declaration of Helsinki. The study will also be carried out in keeping with applicable local law(s) and regulation(s).

Strict adherence to all specifications laid down in this protocol is required for all aspects of study conduct; the investigator may not modify or alter the procedures described in this protocol.

Modifications to the study protocol will not be implemented by the investigator without discussion and agreement by Taiho. However, the investigator may implement a deviation from, or a change of, the protocol to eliminate an immediate hazard(s) to the trial subjects without prior IEC/IRB/Taiho approval/favorable opinion. As soon as possible, the implemented deviation or change, the reasons for it and, if appropriate, the proposed protocol amendment should be submitted to the IEC/IRB/head of medical institution. Any deviations from the protocol must be explained and documented by the investigator.

The Principal Investigator is responsible for the conduct of the clinical trial at the site in accordance with Title 21 of the Code of Federal Regulations and/or the Declaration of Helsinki. The Principal Investigator is responsible for personally overseeing the treatment of all study patients. The Principal Investigator must assure that all study site personnel, including sub-investigators and other study staff members, adhere to the study protocol and all FDA/GCP/NCI regulations and guidelines regarding clinical trials both during and after study completion.

The Principal Investigator will be responsible for assuring that all the required data will be collected and properly documented.

11.2 Subject Information and Consent

Each subject/legal representative or proxy consenter will have ample time and opportunity to ask questions and will be informed about the right to withdraw from the study at any time without any disadvantage and without having to provide reasons for this decision.

Only if the subject/legal representative or proxy consenter voluntarily agrees to sign the informed consent form and has done so, may he/she enter the study. Additionally, the investigator and other information provider (if any) will personally sign and date the form. The subject/legal representative or proxy consenter will receive a copy of the signed and dated form.

The signed informed consent statement is to remain in the investigator site file or, if locally required, in the patient's note/file of the medical institution.

In the event that informed consent is obtained on the date that baseline study procedures are performed, the study record or subject's clinical record must clearly show that informed consent was obtained prior to these procedures.

1. If the patient is not capable of providing a signature, a verbal statement of consent can also be given in the presence of an impartial witness (independent of Taiho, and the investigator). This is to be documented by a signature from the informing physician as well as by a signature from the witness.

2. For adults under legal protection, consent shall be given by the legal guardian(s). The consent of an adult under legal protection shall also be requested where such a person is able to express his/her own will. His/her refusal or the withdrawal of his/her consent may not be disregarded.
3. In emergency situations, when prior consent of the patient is not possible, the consent of the patient's legal representative(s) or proxy consenter, if present, should be requested. The patient should be informed about the study as soon as possible and his/her consent to continue the study should be requested.

The informed consent form and any other written information provided to subjects/legal representatives or proxy consenters will be revised whenever important new information becomes available that may be relevant to the subject's consent, or there is an amendment to the protocol that necessitates a change to the content of the subject information and/or the written informed consent form. The investigator will inform the subject/legal representative or proxy consenter of changes in a timely manner and will ask the subject to confirm his/her participation in the study by signing the revised informed consent form. Any revised written informed consent form and written information must receive the IEC/IRB's approval/favorable opinion in advance of use.

11.3 Confidentiality

All records identifying the subject will be kept confidential and, to the extent permitted by the applicable laws and/or regulations, will not be made publicly available.

Should direct access to medical records require a waiver or authorization separate from the subject's statement of informed consent, it is the responsibility of the Investigator to obtain such permission in writing from the appropriate individual.

12. Appendix

APPENDIX A: RECIST Criteria for Measuring Tumor Response Antitumor Effect

Response and progression will be evaluated in this study using the new international criteria proposed by the revised Response Evaluation Criteria in Solid Tumors (RECIST) guideline (version 1.1) (Eisenhauer et al., 2009). Changes in the largest diameter (unidimensional measurement) of the tumor lesions and the shortest diameter in the case of malignant lymph nodes are used in the RECIST criteria.

Definitions

Evaluable for toxicity. All patients will be evaluable for toxicity from the time of their first treatment with ramucirumab or TAS 102.

Evaluable for objective response. Only those patients who have measurable disease present at baseline, have received at least one cycle of therapy, and have had their disease re-evaluated

will be considered evaluable for response. These patients will have their response classified according to the definitions stated below. (Note: Patients who exhibit objective disease progression prior to the end of cycle 1 will also be considered evaluable.)

Disease Parameters

Measurable disease. Measurable lesions are defined as those that can be accurately measured in at least one dimension (longest diameter to be recorded) as ≥ 10 mm with CT scan, MRI or calipers by clinical exam. All tumor measurements must be recorded in millimeters (or decimal fractions of centimeters).

Note: Tumor lesions that are situated in a previously irradiated area might be considered measurable if the lesion has increased in size since the radiation.

Malignant lymph nodes. To be considered pathologically enlarged and measurable, a lymph node must be ≥ 15 mm in short axis when assessed by CT scan (CT scan slice thickness recommended to be no greater than 5 mm). At baseline and in follow-up, only the short axis will be measured and followed.

Non-measurable disease. All other lesions (or sites of disease), including small lesions (longest diameter < 10 mm or pathological lymph nodes with ≥ 10 to < 15 mm short axis), are considered non-measurable disease. Bone lesions, leptomeningeal disease, ascites, pleural/pericardial effusions, lymphangitis cutis/pulmonitis, and abdominal masses (not followed by CT or MRI), are considered as non-measurable.

Target lesions. All measurable lesions up to a maximum of 2 lesions per organ and 5 lesions in total, representative of all involved organs, should be identified as **target lesions** and recorded and measured at baseline. Target lesions should be selected on the basis of their size (lesions with the longest diameter), be representative of all involved organs, but in addition should be those that lend themselves to reproducible repeated measurements. It may be the case that, on occasion, the largest lesion does not lend itself to reproducible measurement in which circumstance the next largest lesion which can be measured reproducibly should be selected. A sum of the diameters (longest for non-nodal lesions, short axis for nodal lesions) for all target lesions will be calculated and reported as the baseline sum diameters. If lymph nodes are to be included in the sum, then only the short axis is added into the sum. The baseline sum diameters will be used as reference to further characterize any objective tumor regression in the measurable dimension of the disease.

Non-target lesions. All other lesions (or sites of disease) including any measurable lesions over and above the 5 target lesions should be identified as **non-target lesions** and should also be recorded at baseline. Measurements of these lesions are not required, but the presence, absence, or in rare cases unequivocal progression of each should be noted throughout follow-up.

Methods for Evaluation of Measurable Disease

All measurements should be taken and recorded in metric notation using a ruler or calipers. All baseline evaluations should be performed as closely as possible to the beginning of treatment and never more than 4 weeks before the beginning of the treatment.

The same method of assessment and the same technique should be used to characterize each identified and reported lesion at baseline and during follow-up. Imaging-based evaluation is preferred to evaluation by clinical examination unless the lesion(s) being followed cannot be imaged but are assessable by clinical exam.

Clinical lesions. Clinical lesions will only be considered measurable when they are superficial (e.g., skin nodules and palpable lymph nodes) and ≥ 10 mm diameter as assessed using calipers (e.g., skin nodules). In the case of skin lesions, documentation by color photography, including a ruler to estimate the size of the lesion, is recommended.

Conventional CT and MRI. This guideline has defined measurability of lesions on CT scan based on the assumption that CT slice thickness is 5 mm or less. If CT scans have slice thickness greater than 5 mm, the minimum size for a measurable lesion should be twice the slice thickness. MRI is also acceptable in certain situations (e.g., for body scans).

Use of MRI remains a complex issue. MRI has excellent contrast, spatial, and temporal resolution; however, there are many image acquisition variables involved in MRI, which greatly impact image quality, lesion conspicuity, and measurement. Furthermore, the availability of MRI is variable globally. As with CT, if an MRI is performed, the technical specifications of the scanning sequences used should be optimized for the evaluation of the type and site of disease. Furthermore, as with CT, the modality used at follow-up should be the same as was used at baseline and the lesions should be measured/assessed on the same pulse sequence. Ideally, the same type of scanner should be used and the image acquisition protocol should be followed as closely as possible to prior scans. Body scans should be performed with breath-hold scanning techniques, if possible.

Response Criteria Evaluation of Target Lesions

Complete Response (CR): Disappearance of all target lesions. Any pathological lymph nodes (whether target or non-target) must have reduction in short axis to <10 mm.

Partial Response (PR): At least a 30% decrease in the sum of the diameters of target lesions, taking as reference the baseline sum diameters.

Progressive Disease (PD): At least a 20% increase in the sum of the diameters of target lesions, taking as reference the smallest sum on study (this includes the baseline sum if that is the smallest on study). In addition to the relative increase of 20%, the sum must also demonstrate an absolute increase of at least 5 mm. (Note: the appearance of one or more new lesions is also considered progression.)

Stable Disease (SD): Neither sufficient shrinkage to qualify for PR nor sufficient increase to

qualify for PD, taking as reference the smallest sum diameters while on study.

Evaluation of Non-Target Lesions

Complete Response (CR): Disappearance of all non-target lesions and normalization of tumor marker level. All lymph nodes must be non-pathological in size (<10 mm short axis).

Non-CR/Non-PD: Persistence of one or more non-target lesion(s).

Progressive Disease (PD): Appearance of one or more new lesions and/or unequivocal progression of existing non-target lesions. Unequivocal progression should not normally trump target lesion status. It must be representative of overall disease status change, not a single lesion increase.

Although a clear progression of “non-target” lesions only is exceptional, the opinion of the treating physician should prevail in such circumstances, and the progression status should be confirmed at a later time by the Principal Investigator.

Evaluation of Best Overall Response

The best overall response is the best response recorded from the start of the treatment until disease progression/recurrence (taking as reference for progressive disease the smallest measurements recorded since the treatment started). The patient's best response assignment will depend on the achievement of both measurement and confirmation criteria.

For Patients with Measurable Disease (i.e., Target Disease)

Target Lesions	Non-Target Lesions	New Lesions	Overall Response
CR	CR	No	CR
CR	Non-CR/Non-PD	No	PR
CR	Not evaluated	No	PR
PR	Non-CR/Non-PD/not evaluated	No	PR
SD	Non-CR/Non-PD/not evaluated	No	SD
PD	Any	Yes or No	PD
Any	PD*	Yes or No	PD
Any	Any	Yes	PD

*In exceptional circumstances, unequivocal progression in non-target lesions may be accepted as disease progression.

Duration of Response

Duration of overall response: The duration of overall response is measured from the time measurement criteria are met for CR or PR (whichever is first recorded) until the first date that

recurrent or progressive disease is objectively documented (taking as reference for progressive disease the smallest measurements recorded since the treatment started).

The duration of overall CR is measured from the time measurement criteria are first met for CR until the first date that progressive disease is objectively documented.

Duration of stable disease: Stable disease is measured from the start of the treatment until the criteria for progression are met, taking as reference the smallest measurements recorded since the treatment started, including the baseline measurements.

Progression-Free Survival (PFS)

PFS is defined as the duration of time from start of treatment to time of progression or death, whichever occurs first

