This is a single institutional phase II single arm, two-stage trial using ramucirumab and TAS 102 in subjects with advanced, refractory gastric or GEJ adenocarcinoma. In the first stage, 15 patients will be accrued. If 7 or more out of 15 survive 6 months or more, an additional 10 patients will be accrued for a total of 25 patients. TAS 102 and ramucirumab will be concurrently administered with ramucirumab 8mg/kg every 2 weeks (Q2W) and TAS 102 at doses of 35 mg/m² twice a day (Details on 5.1). After 2 cycles (1 cycle=28 days), response and progression will be evaluated using Response Evaluation Criteria in Solid Tumors (RECIST) guidelines (version 1.1). Primary endpoint is 6 month overall survival. We will continue to recruit patients during interim analysis. Although no dose limiting toxicities of TAS 102 plus bevacizumab which has almost same mechanisms of action and safety profiles as ramucirumab were observed in a previous phase 1/2 study ⁴⁴, unexpected toxicities can occur with this combination. Therefore, we will closely monitor first 6 patients for first 28 days. If none or one of these patients has a dose limiting toxicity, we will continue without dose adjustment. If ≥ 2 patients has a dose limiting toxicity, the dose will be decreased to level -1 (TAS 102: 30mg/m² twice a day and ramucirumab: 8mg/kg Q2W, details in table 1), and 6 additional patients will be enrolled at dose level -1. If none or one of these patients has a dose limiting toxicity at dose level -1 for first 28 days, we will use dose level -1. If ≥ 2 patients has a dose limiting toxicity at dose level -1, the study will be terminated. First 6 or 12 patients depending on dose limiting toxicities will be used for primary and secondary objectives. Dose limiting toxicity is defined as a grade 3 or higher non-hematological toxicity excluding controllable nausea, vomiting, hypertension, diarrhea, transient electrolyte abnormalities and alopecia; grade 4 neutropenia

lasting 7 days or more; grade 3 or higher febrile neutropenia; grade 4 thrombocytopenia.

4. Eligibility

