4.1 Inclusion Criteria

1. Histologically confirmed diagnosis of gastric and GEJ adenocarcinoma
2. Measurable or non-measurable disease by Response Evaluation Criteria in Solid Tumors (RECIST) 1.1. Stage IV or recurrent disease is required. An irradiated lesion is considered evaluable only if it has shown enlargement since the completion of last radiation.
3. Patients must have received and progressed with prior therapy. Prior therapy with ramucirumab is not allowed. Patients must have recovered from the toxic effects of the previous anti-cancer chemotherapy (with the exception of alopecia).
4. ECOG Performance Score 0 or 1
5. Estimated life expectancy > 3 months
6. Adequate bone marrow, liver and renal function as assessed by the following:
 - o Hemoglobin > 8.0 g/dl
 - o Absolute neutrophil count (ANC) > 1,000/mm³ independent of growth factor support
 - o Platelet count > 100,000/mm³
 - o Total bilirubin < 1.5 times ULN unless bilirubin rise is due to Gilbert's syndrome or of non-hepatic origin
 - o AST, ALT and Alkaline Phosphatase \leq 2.5 times the ULN (\leq 5 x ULN for patients with liver involvement)
 - o Creatinine clearance \geq 30 ml/min
7. Patients must not have had chemotherapy, major surgery, monoclonal antibody therapy or experimental therapy within the 28 days prior to the start of TAS 102 administration.
8. Women of childbearing potential must have a negative serum pregnancy test performed within 7 days prior to the start of study drug. Post-menopausal women (defined as no menses for at least 1 year) and surgically sterilized women are not required to undergo a pregnancy test.
9. Subjects (men and women) of childbearing potential must agree to use adequate contraception beginning at the signing of the ICF until at least 4 months for both females and males after the last dose of study drug. The definition of adequate contraception will be based on the judgment of the principal investigator or a designated associate.
10. Subjects must be able to understand and be willing to sign the written informed consent form. A signed informed consent form must be appropriately obtained prior to the conduct of any trial-specific procedure. Subjects must be willing and able to comply with scheduled visits, treatment schedule, laboratory testing, and other study requirements.

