6.7 End of Treatment Visit and Follow up

End of Treatment Visit

- History and assessment to include brief examination, vital signs (heart rate, respiration rate, temperature and BP) and review of systems
- Toxicity/AE assessment
- ECOG Performance Status Assessment
- Hematology (hemoglobin, HCT, RBC, WBC with differential (neutrophils, bands, lymphocytes, monocytes, eosinophils and basophils) and platelet count
- Chemistry (ALT, AST, AP, total bilirubin, direct bilirubin, LDH, glucose, calcium, phosphate, magnesium, bicarbonate, sodium)
- UA
- Tumor measurement/disease assessment according to RECIST 1.1 (please see Appendix B) may be conducted if it has not been performed within the last 4 weeks.

Safety Follow-Up Visit

The mandatory Safety Follow-Up Visit should be conducted approximately 30 days after the last dose of trial treatment. All AEs that occur prior to the Safety Follow-Up Visit should be recorded. Subjects with an AE of Grade > 1 will be followed until the resolution of the AE to Grade 0-1 or until the beginning of a new anti-neoplastic therapy, whichever occurs first. SAEs that occur within 90 days of the end of treatment or before initiation of a new anti-cancer

treatment should also be followed and recorded.

Survival Follow-up

Once a subject experiences confirmed disease progression or starts a new anti-cancer therapy, the subject moves into the survival follow-up phase for 6 months and should be contacted by telephone every 12 weeks to assess for survival status until death, withdrawal of consent, or the end of the study, whichever occurs first.

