6.8 Calendar

	Screening within 28 days of C1D1 ^m	Cycle 1 Day 1 ± 3 days and subsequent cycles	Cycle 1 day 15 ± 3 days	Cycle X day 1 ± 5 day	Cycle X day 15 ± 5 day	End of treatment visit ⁿ	Safety follow-up	Survival follow-up
Complete History/Physical^a	X							
History & Assessment^b		X	X	X		X	X	
Toxicity Notation		X	X	X		X	X	
ECOG	X	X	X	X		X		
ECG	X							
Tumor Measurement/ Disease Assessment^c	X			X		X		
Hematology^d	X	X	X	X	X	X		
Chemistry^e	X	X	X	X	X	X		
Coagulation^f	X							
Urinalysis^g	X	X		X		X		
24hr urine protein^h			X	X	X	X		
Hepatitis and HIV Screeningⁱ	X							
Serum	X							

Pregnancy, if applicable j								
Survival f/u k								X
Diary – Issued/Retur- ned¹		X		X				

- a. *Complete medical history and physical examination* including demographics, surgery, therapies, medications, smoking, alcohol history, co-existing diseases, allergy, NYHA classification, vital signs (heart rate, respiration rate, temperature and BP), height, weight and review of systems.
- b. *History and assessment* including brief examination, vital signs and review of systems. Note all toxicities and adverse events, using CTCAE version 5.
- c. Tumor assessment using CT or MRI (at investigator's discretion) will be collected at screening, after every 3 cycles, and as clinically indicated. Tumor response will be assessed using RECIST 1.1 criteria. Tumor measurement/disease assessment should be performed within 7 days at the beginning of every 3rd cycle.
- d. Hemoglobin, hematocrit, red blood cell count, white blood cell count with differential (neutrophils, bands, lymphocytes, monocytes, eosinophils and basophils) and platelet count.
- e. ALT, AST, alkaline phosphatase, total bilirubin, direct bilirubin, LDH, creatine kinase, lipase, amylase glucose, calcium, phosphate, magnesium, bicarbonate, sodium, potassium, chloride, creatinine, blood urea nitrogen (BUN), total protein and albumin.
- f. PT-INR and aPTT.
- g. Urinalysis including blood, glucose, protein, specific gravity. If dipstick or routine urinalysis indicates proteinuria $\geq 2+$, a 24-hour urine collection must be obtained in 2 weeks.
- h. If necessary
- i. Hepatitis B surface antigen, surface antibody, core antigen and Hepatitis C antibody
- j. Pregnancy test will be performed at baseline for WOCBP and then only as clinically indicated

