- k. Can be performed over the phone. After off treatment following disease progression, physical assessments (with lab tests performed at the discretion of the treating investigator) should take place every 3 months for up to two years or death.
- l. A diary card will be issued on day 1 of each cycle and the issued diary card will be returned on subsequent cycle
- m. Radiologic tests (CT scan or MRI) performed up to 4 weeks prior to obtaining informed consent can be used for screening purposes.

- n. Restaging imaging only to be performed if not done within the last 4 weeks

7. Assessment types

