9.2 Determination of sample size

The primary objective of this study is overall survival at 6 months. Overall survival (OS) will be defined as the time from starting on trial to date of death due to any cause. Dropouts/screen failures defined in section 4.3.1. Patients will be considered inevaluable for the primary endpoint of 6 months of overall survival if they are not able to complete first cycle or if they are lost follow-up prior to 6 months from starting on trial except death. Inevaluable patients will be replaced. The study will test the null hypothesis of $\leq 45\%$ of OS at 6 month against the alternative of $\geq 70\%$ of OS at 6 month. The sample size was determined based on the Simon's two-stage minimax design. With one-sided 10% of type I error rate and 90% power, a sample of evaluable 25 patients will be evaluated; 15 in first stage and additional 10 patients in second stage. If 7 or more out of 15 survive 6 months or more, the study goes on the second stage. The experimental treatment will be deemed to have good activity if ≥ 15 out of 25 patients survive 6 months or more. We will continue to recruit patients during interim analysis

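### The only response population in the plan leaves out treated patients who were never re-scanned, so the objective response rate would be overstated

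*Combined protocol and SAP*

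**What the plan says.** Section 9.3 defines the ORR as complete plus partial responses by RECIST 1.1, with a reference to Appendix A, and adds that "ORR will be reported with 95% CI computed by the Clopper-Pearson method". It does not say which patients form the denominator.

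Appendix A (Definitions) has the only statement of who counts for response: "Only those patients who have measurable disease present at baseline, have received at least one cycle of therapy, and have had their disease re-evaluated". A note keeps patients who show objective progression during the first cycle. Nothing is said about other patients without a post-baseline assessment.

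Other provisions that bear on the point:

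- Section 4.1 admits "Measurable or non-measurable disease by Response Evaluation Criteria in Solid Tumors (RECIST) 1.1", so the ORR base may be below 25 before any scan is missed.
- Section 9.2: "Patients will be considered inevaluable for the primary endpoint of 6 months of overall survival if they are not able to complete first cycle". These patients are replaced. Section 4.3.1 permits replacement after any withdrawal from treatment. Section 4.3.2 requires it for patients who leave without a response evaluation, unless the cause was a drug-related adverse event or progression.
- The first scan is placed differently in different sections. Section 3: "After 2 cycles (1 cycle=28 days), response and progression will be evaluated". Section 6.8, footnote c: scans "will be collected at screening, after every 3 cycles, and as clinically indicated".
- The Section 6.8 calendar marks a tumor assessment at the end-of-treatment visit, with footnote n: "Restaging imaging only to be performed if not done within the last 4 weeks". Section 6.7 is weaker and says the assessment "may be conducted if it has not been performed within the last 4 weeks".

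**The concern.** A Clopper-Pearson interval needs a denominator, and Appendix A supplies the only candidate. It requires re-evaluation, so membership depends on what happens after treatment starts. The patients it removes are those least likely to have benefited: early deaths, clinical deterioration without imaging, and early stops for toxicity. None of them can be recorded as a responder, so leaving them out pushes the ORR one way, in favour of the regimen. The confidence interval does not show this, because it describes sampling error within whichever set was chosen. A single-arm trial also has no control group in which the same exclusion would operate.

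Replacement adds a second gap. No section says whether a treated patient who was later replaced stays in the ORR denominator. The best-response table in Appendix A does not help: it has no outcome for a patient whose target lesions were not assessed and who has no documented progression elsewhere.

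**Working it through.** **The plan's own figures.** The document gives no expected ORR, precision target or missing-scan rate, so there is no ORR figure to reproduce. The only design figure is the two-stage rule for 6-month survival (continue with at least 7 of 15, success with at least 15 of 25, 45% against 70%). It reproduces with an exact one-sided type I error of 0.0951 and power of 0.9004. Nothing below touches it.

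**When patients can be lost.** With 28-day cycles, the first scheduled scan falls at 2 × 28 = 56 days (week 8) under Section 3 and the Cycle 3 Day 1 label in Section 6.6. Under the three-cycle wording of footnote c it falls at 3 × 28 = 84 days (week 12). A patient who leaves before then is evaluable only if an unscheduled or end-of-treatment assessment is done. Those who leave during cycle 1 need objective progression.

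**Formula.** Let N be treated patients with measurable disease, r the responders, and d those with no post-baseline assessment.

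- All counted: r/N.
- Appendix A set: r/(N − d).
- Ratio: N/(N − d), which exceeds 1 whenever d > 0 and r > 0.

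**Illustration (a).** Assumptions: 25 treated, none replaced, all with measurable disease, r = 5. Intervals are Clopper-Pearson 95%.

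| d | Estimate | 95% CI | Factor |
|---|---|---|---|
| 0 (all counted) | 5/25 = 20.0% | 6.8–40.7 | 1 |
| 1 | 5/24 = 20.8% | 7.1–42.2 | 25/24 = 1.04 |
| 3 | 5/22 = 22.7% | 7.8–45.4 | 25/22 = 1.14 |
| 5 | 5/20 = 25.0% | 8.7–49.1 | 25/20 = 1.25 |

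**Illustration (b), with replacement.** Assume two patients leave during cycle 1 unassessed and are replaced, so 27 are treated, and 3 of the other 25 are never re-evaluated. Then d = 2 + 3 = 5. Counting all gives 5/27 = 18.5% (6.3–38.1). The Appendix A set gives 5/22 = 22.7% (7.8–45.4). The factor is 27/22 = 1.23.

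**Fewer with measurable disease.** With N = 20 and r = 5, counting all gives 25.0% (8.7–49.1). Dropping 3 gives 5/17 = 29.4% (10.3–56.0), and dropping 5 gives 5/15 = 33.3% (11.8–61.6), a factor of 20/15 = 1.33.

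**No responders.** The estimate stays at 0%. Only the upper limit moves, from 13.7% (0/25) to 15.4% (0/22).

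**The opposite case.** A patient who stops within cycle 1 but is later scanned as responding also fails the one-cycle condition, and excluding that patient would lower the ORR. This is possible but unlikely.

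**The case against.** The strongest reply is that the Appendix A reference in Section 9.3 follows the words on RECIST criteria, so it may point to the response definitions and not to an analysis set. That stands as far as it goes: the denominator is inferred, not stated. But no other response population exists in the document, and Appendix A says that only its evaluable patients have their response classified. A different intention would still have to be written down.

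Second, an evaluable set declared in advance for a descriptive secondary endpoint is open to view and is not an internal contradiction. That is true, but declaring the exclusion does not remove its direction.

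Third, several provisions limit the loss. Entry requires ECOG 0 or 1 and an estimated life expectancy above 3 months. Scans are allowed when clinically indicated, the calendar marks an end-of-treatment assessment, and two rows of the response table can classify a patient whatever the target-lesion status. These narrow the problem. They do not cover a patient who dies or is too ill to scan, and the two table rows lead only to progressive disease.

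Fourth, the inevaluability rule in Section 9.2 concerns 6-month survival, not response. That is correct. Cycle-1 exits leave the ORR through Appendix A's one-cycle condition, and Section 9.2 matters only because it raises the number treated without saying how replaced patients are counted.

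Finally, the shift is small beside the interval width, and every count used to illustrate it is assumed. Both are true.

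**Conclusion.** The concern holds. Read in the natural way, the plan drops treated patients who cannot be responders, which biases the ORR upward whenever at least one such patient and at least one responder exist. The responder with an incomplete first cycle is the only exception. The size is unknown from the documents. Over the assumed ranges (20 to 27 treated patients with measurable disease, 1 to 5 unassessed), the ORR is inflated by a factor of 1.04 to 1.33. In the middle case, 20.0% becomes 22.7%.

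The conclusion rests on the Appendix A set being the denominator. If it is not, the plan has no stated ORR denominator, and the same text is needed. The consequence is confined to a descriptive secondary endpoint and does not reach the 6-month survival decision. The plan should be changed because the bias favours the regimen and is cheap to remove.

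**What to change.** In Section 9.3 and Appendix A:

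- Define the main ORR denominator as all patients with measurable disease at baseline who received at least one dose of study drug, including any later replaced. State that this number may differ from 25.
- Count patients with no post-baseline assessment as non-responders.
- Compute the Clopper-Pearson interval on that set.
- Report the Appendix A response-evaluable rate as a labelled supportive figure, with the number of patients left out and the reasons.

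This costs a few sentences and needs no new data or scans. The reported ORR will be slightly less favourable if any treated patient goes unassessed. Settling it before results are known also removes a choice of denominator after the fact.
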